12. CLINICAL PHARMACOKINETIC AND PHARMACODYNAMIC ANALYSES

12.1 Pharmacokinetic Methods

Individual PK data will be listed, and listing(s) will be based on the Safety Analysis Set; all summaries and analyses of the PK data will be based on the PK Set.

12.1.1 Concentration Data

Blood samples will be drawn from each subject during this study for the determination of plasma concentrations of lanadelumab. Serial blood samples will be collected during the in-house treatment period on Days 1 to 5 for PK analysis at predose, and at 8, 24, 48, 72, and 96 hours after administration of the investigational product. One postdose blood sample will be also drawn from each subject on Days 7, 14, 21, 28, 42, 56, 84 and 112 for the determination of lanadelumab concentrations. Actual sampling times post-dose will be considered protocol deviations where the sample deviated from nominal collection time by more than ± 5 minutes within the first 4 hours, ± 15 minutes between 4 and 96 hours, ± 1 day between Days 7 and 21, ± 2 days between Days 28 and 56, and ± 3 days on Days 84 and 112. Samples collected outside these windows will be flagged in data listings. Plasma concentrations of lanadelumab will be measured using a validated analytical method.

Individual lanadelumab plasma concentrations will be listed by ethnic group, subject, overall ADA status, day, and time based on the Safety Analysis Set and summarized by ethnic group and time, and separately by ethnic group, overall ADA status and nominal time, all based on the PK Set. Summaries will include: number of subjects (n), arithmetic mean, SD, percent coefficient of variation (%CV), median, minimum, maximum, geometric mean, and %CV of geometric mean. In addition, the mean and individual lanadelumab plasma concentration versus time profiles by ethnic group and overall ADA status will be presented in figures on both linear and semi-logarithmic scales. Mean (\pm SD) lanadelumab plasma concentration versus nominal time profiles will be presented for the PK Set using nominal time. All sampling times considered to be protocol deviations will be excluded from summaries and mean plots. Individual lanadelumab plasma concentration versus time profiles will be presented using nominal time based on the Safety Analysis Set.

12.1.2 Handling BLQ Values

The following procedures will be used for lanadelumab plasma PK concentrations below the lower limit of quantification (LLOQ):

- Samples that are below limit of quantification (BLQ) will be reported as $<$ LLOQ in the data listings, where LLOQ is replaced by the actual value for LLOQ for specific PK assay.

- Samples that are BLQ are treated as zero in the calculation of summary statistics (e.g. mean, SD, etc.) for the plasma PK concentrations at individual time points. Geometric mean and %CV of geometric mean will be set to missing where zero values exist.
- Mean concentrations are reported as zero if all values are BLQ or zero, and no other descriptive statistics are reported. If the calculated mean (\pm SD) concentration is less than the LLOQ, the value will be reported as calculated. The mean values derived using these concentrations will be used to create the mean plasma concentration versus time plots.
- For calculation of area under the plasma concentration curve (AUC), BLQ values are set equal to zero in the dataset loaded into Phoenix[®] WinNonlin[®] (Certara USA, Inc, Princeton, NJ) for PK analysis. WinNonlin[®] uses the zero values that occur before the first time point with a concentration greater than LLOQ. Values that are BLQ after the first measurable concentration will be set to “missing” in the dataset loaded into WinNonlin[®].
- Missing values will not be imputed.

12.1.3 Pharmacokinetic Parameters

The PK analysis will be conducted using Phoenix[®] WinNonlin[®] (Certara USA, Inc, Princeton, NJ) Version 6.4 or higher. Pharmacokinetic parameters will be determined from the lanadelumab plasma concentration-time data using non-compartmental analysis based on actual sampling times. All samples will be used in the PK analysis regardless of whether they are considered protocol deviations or not.

The PK parameters for lanadelumab will include, but may not be limited to:

- C_{\max} Maximum observed lanadelumab plasma concentration
- t_{\max} Time of maximum observed lanadelumab plasma concentration
- $AUC_{0-\text{last}}$ Area under the lanadelumab plasma concentration-time curve from time zero to the last quantifiable plasma concentration, calculated using the linear-up/log-down trapezoidal rule

In this method, the linear trapezoidal method of calculation is used for each incremental trapezoid and the log trapezoidal rule for each decremental trapezoid
- $AUC_{0-\infty}$ Area under the lanadelumab plasma concentration-time curve from time zero extrapolated to infinity
- λ_z First order rate constant associated with the terminal (log-linear) portion of the lanadelumab plasma concentration curve

- $t_{1/2}$ Terminal half-life
- CL/F Apparent clearance
- V_z/F Apparent volume of distribution

Body weight-adjusted AUC_{0-last} , $AUC_{0-\infty}$, C_{max} , CL/F, and V_z/F PK parameters will also be determined.

12.2 Statistical Analysis of Pharmacokinetic Parameters

Descriptive statistical analysis of PK parameters will be based on the PK Set. The plasma PK parameters of lanadelumab will be summarized by ethnic group, and separately by ethnic group and overall ADA status. Summaries will include: n, arithmetic mean, SD, %CV, median, minimum, maximum, geometric mean, and %CV of geometric mean. In addition, 95% confidence intervals (CIs) for PK parameters will be provided. Listing of individual plasma PK parameters of lanadelumab will be provided based on the Safety Analysis Set. Individual (observed) and body weight-adjusted PK parameters (y-axis) versus body weight (x-axis) by ethnic group and overall ADA status will be presented in figures on both linear and semi-logarithmic scales for AUC_{0-last} , $AUC_{0-\infty}$, C_{max} , CL/F, and V_z/F .

Following ln-transformation, the PK parameters C_{max} , AUC_{0-last} , and $AUC_{0-\infty}$, will be analyzed using an analysis of variance (ANOVA) model, for estimation purposes. No formal hypothesis testing will be performed. The model will include ethnic group as a fixed effect. Point estimates and their associated 90% CIs will be constructed for the differences in the ln-transformed parameters. The point estimates and their associated 90% CIs will be then back-transformed to provide point estimates for the ratio (Japanese Subjects/Caucasian Subjects) of geometric least squares means and associated 90% CIs on the original scale.

To assess the impact of overall ADA status on the ethnic group comparison, if data permits, a sensitivity analysis will be performed by repeating the above ANOVA analyses by overall ADA status.

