2.5 Determination of Sample Size

The planned sample size for this study is 32 subjects: 16 subjects of Japanese descent and 16 matched non-Hispanic Caucasian subjects.

Assuming a 25% dropout rate (based on previous clinical experience), the sample size ensures approximately 24 subjects (12 Japanese and 12 matched non-Hispanic Caucasians) complete the study, and 24 subjects are evaluable for PK analysis purposes. The sample size is considered adequate for the primary objective of the study (defined in [Section 3](#)) and therefore adequate for providing reliable estimates of PK parameters, and similarly for the secondary objective.

No formal statistical hypothesis will be tested. The sample size was based on clinical judgment, precedent PK studies of similar design, and similar subject population, not on statistical considerations such as study power. Any subject who prematurely discontinues the study, whether part of a matched pair or is not yet matched, may be replaced at the discretion of the study sponsor to ensure there are approximately 12 evaluable subjects in each ethnic group for PK analysis purposes.

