4.3 Pharmacokinetic Set

The PK Set will consist of all subjects in the Safety Analysis Set who have at least 1 evaluable postdose PK concentration value. All PK analyses will be based on the PK Set.

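### No profile-completeness rule for AUC0-last: truncated values from early dropouts enter the Japanese/Caucasian ratio, at a cost mainly in precision

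*SAP*

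**What the plan says.** - **Who is analysed.** SAP 4.3: "The PK Set will consist of all subjects in the Safety Analysis Set who have at least 1 evaluable postdose PK concentration value". Every PK analysis uses this set. Here *evaluable* describes a concentration, not a profile.
- **What AUC0-last is.** SAP 12.1.3 takes the area "from time zero to the last quantifiable plasma concentration, calculated using the linear-up/log-down trapezoidal rule". There is no common end time.
- **BLQ and missing values.** SAP 12.1.2: "Values that are BLQ after the first measurable concentration will be set to" missing, and "Missing values will not be imputed".
- **The comparison.** SAP 12.2: "Descriptive statistical analysis of PK parameters will be based on the PK Set". Log-transformed Cmax, AUC0-last and AUC0-∞ go into an ANOVA with ethnic group as the only effect, giving a ratio of geometric means with a 90% CI. SAP 20 (Table 14.2.5.5) confirms the PK Set.
- **The planning assumption.** SAP 2.5 assumes 25% dropout, so that about 24 of 32 subjects "complete the study, and 24 subjects are evaluable for PK analysis purposes". Subjects who discontinue "may be replaced at the discretion of the study sponsor to ensure there are approximately 12 evaluable subjects in each ethnic group".
- **What is absent.** Neither document sets a minimum last sampling time, a minimum number of samples or a partial AUC to a common day. SAP 17 adds the ANOVA but no completeness rule.

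**The concern.** SAP 2.5 treats the 24 PK-evaluable subjects as the completers. Under SAP 4.3 and 12.2, all 32 dosed subjects can enter the AUC0-last ratio, including about 8 who left early. Sampling is in-house to 96 hours, so the exposed window runs from Day 5 to about Day 42. A subject last sampled on Day 14 has a small AUC0-last because sampling stopped, not because exposure was low.

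Protocol 2.1 says the study is to show whether non-Japanese data can be extrapolated to Japanese patients. The geometric mean ratio with its 90% CI is the only between-group estimate planned, and AUC0-last is one of its three parameters. Artificially low values inflate the residual variance and widen the interval. If they fall unevenly between the groups, they also move the point estimate in that trial.

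The BLQ convention is not the cause. A profile that ends because the drug has become unquantifiable is essentially complete; one that ends because the subject left is not.

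**Working it through.** **1. The plan's own figure.** 32 × (1 − 0.25) = 24, or 16 × 0.75 = 12 per group. This reproduces. There is no power figure to check.

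**2. Assumptions not in the documents.** One-compartment SC profile, ka 0.4/day, half-life 14 days (range 10–20), CV 30%, 16 per group, true ratio 1.00. The sampling times are those of SAP 12.1.1, with the dose on Day 1, and the AUC uses the linear-up/log-down rule.

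**3. AUC0-last of a dropout as a share of the Day 112 value**

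| Last sample | Half-life 14 d | Range 20 d to 10 d |
|---|---|---|
| Day 7 | 17% | 12–22% |
| Day 14 | 40% | 31–51% |
| Day 28 | 70% | 58–81% |
| Day 56 | 93% | 86–97% |

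**4. Dropout timing.** Two patterns were used:
- *Calendar*: uniform over Days 5–112. The last sample is at or before Day 28 in (42 − 5)/107 = 35% of dropouts.
- *Per visit*: uniform over the eight last-sample slots from 96 h to Day 84. This is front-loaded, with 5/8 = 62.5% at or before Day 28.

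**5. Interval width, 4 dropouts per group.** Half-width = t(0.95, n1+n2−2) × s × √(1/n1 + 1/n2).

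For 12 completers per group, s = √ln(1 + 0.30²) = 0.294, so the half-width is 1.717 × 0.294 × √(2/12) = 0.206. The simulated mean is 0.203. Simulated means for all the sets:

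| Dropout timing | Full PK Set | Completers | Last sample at or after Day 56 |
|---|---|---|---|
| Calendar | 0.25 | 0.203 | 0.188 (28 subjects) |
| Per visit | 0.36 | 0.203 | 0.195 (26 subjects) |
| All at Day 56 or 84 | 0.176 | 0.204 | same as full set (32 subjects) |

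The subject counts are 32 − 8 × (1 − 56/107) = 28 and 32 − 8 × 6/8 = 26. For a ratio of 1.00, half-widths of 0.25 and 0.36 give intervals of 0.78–1.28 and 0.70–1.43. Half-widths of 0.188 and 0.195 give 0.83–1.21 and 0.82–1.22.

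Against completers, the full set is 22% wider (calendar; 13–35% over half-lives of 10–20 days) or 76% wider (per visit; 56–99%). Raising the CV from 25% to 40% moves these from 32% to 10% and from 102% to 49%.

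**6. Is the ratio biased?** With independent 25% dropout in both groups and the same timing, the simulated full-set ratio averages 1.00 and 90% CI coverage is about 90% under both patterns. Chance imbalance is already inside the wider interval.

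**7. A given uneven trial.** The mean ln share per dropout is m = −0.349 (calendar) or −0.782 (per visit). With 6 Japanese and 2 Caucasian dropouts, the ratio is exp(m × 4/16) = 0.92 or 0.82. With a 5/3 split it is exp(m × 2/16) = 0.96 or 0.91. From two Binomial(16, 0.25) counts, the numbers differ by 2 or more with probability 54% and by 4 or more with probability 15%, in either direction.

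**8. Replacement.** At 4/4, 12 per group complete and none is needed. At 6/2 with two Japanese replacements, the ratio is exp(m × (6/18 − 2/16)) = 0.93 or 0.85. Replacement adds subjects but removes no truncated value.

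**The case against.** The strongest case is that this is an estimation study with no test or margin, and SAP 1 disclaims formal between-group comparisons. Cmax and AUC0-∞ ratios stand beside AUC0-last. Draw times, concentrations and individual profiles are listed or plotted, so a truncated profile can be seen. The size depends wholly on assumed dropout timing, and late dropout makes the full set better than a completers-only analysis. Much of this stands. It limits the weight of the point but does not supply the missing rule, and choosing exclusions after seeing open-label group results is what a written rule prevents.

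Two stronger readings are tempting, and neither is supported.

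- *The plan biases the ratio.* A reader might infer this from the 0.92 and 0.82. Those figures are conditional on a 6/2 split. Systematic bias needs dropout that truly differs by ethnic group, and both documents plan the same 25% and the same 12 completers in each.
- *Only AUC0-last is affected, so AUC0-∞ is a safe fallback.* SAP 12.1.3 gives no acceptance rule for AUC0-∞ either: no minimum number of terminal points and no limit on the extrapolated share. Whether an early dropout contributes an AUC0-∞, and how much of it is extrapolated, is therefore not settled by the text.

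**Conclusion.** The gap is certain from the text, and following the plan exactly gives a worse AUC0-last estimate whenever some subjects leave before about Day 42. The harm is mainly lost precision: a half-width of about 0.25 to 0.36 instead of 0.19 to 0.20 under the stated assumptions, and no loss if all dropout falls at Day 56 or later. The ratio is unbiased on average when dropout behaves alike in both groups, although an uneven split moves the estimate in that trial. Because no test or margin is attached, the effect is on the estimate and its interval only. This is a moderate point that should be fixed. Confidence in its size is medium, because half-life, absorption rate, CV and dropout timing are all assumed.

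**What to change.** Before database lock, add to SAP 12.2 and list in SAP 17:

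> AUC0-last enters the summaries and the ANOVA only if (a) the last quantifiable concentration is at or after the Day 56 visit, or the first sample taken after it was BLQ with no more than one scheduled sample missed in between, and (b) no more than two consecutive scheduled samples before the last quantifiable one are missing. Other AUC0-last values are listed only. The analysis on the full PK Set is reported as a sensitivity analysis.

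The BLQ condition keeps true fast eliminators. The sponsor should confirm the cut-off visit and allowed gaps from the half-life and LLOQ it already knows, without reference to group results. SAP 4.3 can stay as it is. An acceptance rule for AUC0-∞ should be stated as well.

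**Cost.** One rule, one analysis flag and one extra table run; no new visits or subjects. About 4 to 6 of 32 subjects leave the AUC0-last model, so 26–28 remain, above the 24 planned. The exclusion assumes that dropout is unrelated to exposure. If dropouts had exposure 20% lower or 25% higher, the error at a 6/2 split would be about 1–4%, against 8–18% for the full set. The sensitivity analysis helps to check this.

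**Secondary.** Protocol 4.5 asks discontinued subjects to attend Day 112 where possible, while the schedule footnote rules out PK samples for early discontinuation. The footnote may cover only the early-discontinuation visit. The two should be reconciled on whether such a subject gives a Day 112 PK sample. If one is taken, truncation becomes a long gap in the profile, which clause (b) covers when more than two consecutive samples are missing.

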12.3 Pharmacodynamic Methods

Individual PD data will be listed, and listing(s) will be based on the Safety Analysis Set; all summaries and analyses of the PD data will be based on the PD Set.

12.3.1 Pharmacodynamic Data

Blood samples will be drawn from each subject during this study for the determination of inhibition of pK_{al} activity and plasma cHMWK levels. Serial blood samples will be collected during the in-house treatment period on Days 1 to 5 for PD analysis at predose, and at 8, 24, 48, 72, and 96 hours after administration of the investigational product. Post-dose blood samples will be also drawn from each subject on Days 7, 14, 21, 28, 42, 56, 84 and 112 for the determination of inhibition of pK_{al} activity and plasma cHMWK levels. Actual sampling times post-dose will be considered protocol deviations where the sample deviated from nominal collection time by

more than ± 5 minutes within the first 4 hours, ± 15 minutes between 4 and 96 hours, ± 1 day between Days 7 and 21, ± 2 days between Days 28 and 56, and ± 3 days on Days 84 and 112. Samples collected outside these windows will be flagged in data listings. The pK_{al} activity and plasma cHMWK levels will be measured using validated analytical methods.

Individual pK_{al} activity, inhibition of pK_{al}, and plasma cHMWK levels (from both untreated and treated samples (including intact 110 kDa, 56 kDa, 46 kDa and %cHMWK) will be listed by subject, ethnic group, day, and time based on the Safety Analysis Set and summarized by ethnic group and nominal time based on the PD set. Summaries will include: n, arithmetic mean, SD, %CV, median, minimum, maximum, geometric mean, and %CV of geometric mean. In addition, the mean and individual inhibition of pK_{al} activity and plasma cHMWK levels (%cHMWK from treated samples only) versus nominal time by ethnic group will be presented in figures on a linear scale. Mean (\pm SD) inhibition of pK_{al} activity and mean (\pm SD) plasma cHMWK levels (treated samples only) versus nominal time will be presented for the PD Set using nominal time. All sampling times considered to be major protocol deviations will be excluded from summaries and mean plots. Individual inhibition of pK_{al} activity and plasma cHMWK levels versus time will be presented using nominal time based on the Safety Analysis Set.

12.3.2 Baseline-adjusted Pharmacodynamic Data

Individual plasma cHMWK levels (treated samples only) will be baseline-adjusted at each time point. Baseline is defined as the predose cHMWK level on Day 1. Baseline-adjusted levels of cHMWK will be calculated by subtracting the appropriate baseline values from the reported laboratory levels for that particular subject. If the baseline-adjusted cHMWK level gives a negative value then the negative level will be used as is for analysis.

Individual baseline-adjusted cHMWK levels (from both untreated and treated samples including intact 110 kDa, 56 kDa, 46 kDa and %cHMWK) will be listed by subject, ethnic group, day, and time based on the Safety Analysis Set and summarized by ethnic group and time based on the PD Set separately for original and baseline-adjusted cHMWK. Summaries will include: n, arithmetic mean, SD, %CV, median, minimum, and maximum. In addition, the mean and individual baseline-adjusted plasma cHMWK levels (treated samples only) versus time by ethnic group will be presented in figures on a linear scale. Mean (SD) baseline-adjusted plasma cHMWK levels (treated samples only) versus time will be presented for the PD Set using nominal time. All sampling times considered to be protocol deviations will be excluded from summaries and mean plots. Individual baseline-adjusted plasma cHMWK levels versus time will be presented using nominal time based on the Safety Analysis Set.

12.3.3 Pharmacodynamic Parameters

Not applicable.

12.4 Statistical Analysis of Pharmacodynamic Parameters

Not applicable.

13. OTHER ANALYSES

No other analyses are planned for this study.

14. INTERIM ANALYSIS

No interim analysis is planned for this study.

15. DATA MONITORING/REVIEW COMMITTEE

No Data Monitoring Committee (DMC) is planned for this study.

16. COMPUTER METHODS

Statistical analyses will be performed using Version 9.3 of SAS[®] or higher on a suitably qualified environment. Phoenix[®] WinNonlin[®] (Certara USA, Inc, Princeton, NJ) Version 6.4 or higher will be used for calculating PK parameters.

17. CHANGES TO ANALYSES SPECIFIED IN PROTOCOL

The following changes have been made to the PK analyses specified in the protocol (dated 27 Nov 2017):

- Inclusion of overall ADA status in PK concentration and parameter listings. Additionally, PK concentrations and parameters will be summarized by overall ADA status.
- Addition of the body weight-adjusted PK parameter $AUC_{0-\infty}$.
- Addition of ANOVA statistical analysis model to evaluate the PK of lanadelumab between ethnic groups.
- Removal of the word 'concentration' from the PD population definition, which is not applicable for the PD markers in this study.

No other changes to the analyses specified in the protocol (dated 27 Nov 2017) have been made.

18. DATA HANDLING CONVENTIONS

18.1 General Data Reporting Conventions

Continuous variables will be summarized using the following descriptive statistics: number of subjects (n), mean, median, SD, minimum, maximum. Unless specified otherwise, summary statistics will be presented to 1 more significant digit than the raw data. The minimum and maximum values will be presented to the same number of decimal places as the raw data; the mean and median will be presented to 1 more decimal place than the raw data; and the SD and standard error will be presented to 2 more decimal places than the raw data. BMI, averaged laboratory results e.g. diastolic/systolic blood pressure and pulse (when taken in triplicate), and derived questionnaire scores will be rounded to 1 decimal place for reporting.

Categorical and count variables will be summarized by the number of subjects and the percent of subjects in each category, as appropriate. Percentages will be presented as whole numbers.

18.2 Derived Efficacy Endpoints

Not applicable.

18.3 Repeated or Unscheduled Assessments of Safety Parameters

If a subject has repeated or unscheduled assessments before the start of investigational product, then the results from the most recent assessment made prior to the start of investigational product will be used as baseline.

If post-baseline assessments are repeated, these will be captured as unscheduled visits, and the value recorded at the scheduled visit will be used for generating descriptive statistics.

All assessments, including unscheduled and repeated assessments, will be presented in the data listings.

